## **BACKGROUND LITERATURE**

---

Endometriosis results from the presence of endometrial cells growing abnormally outside the uterus and affects approximately 10% of reproductive-aged females. Endometriosis can be associated with various types of pain such as: dysmenorrhea (painful cramps with menses), deep dyspareunia (pelvic pain with deep intercourse), dyschezia (painful bowel movements) and chronic pelvic pain. Few studies have explored the association between endometriosis and deep dyspareunia resulting in a limited understanding of how to treat deep dyspareunia. Deep dyspareunia is defined as pelvic pain with deep sexual intercourse and occurs in 50% of women with endometriosis at some time in their sexual lives. Deep dyspareunia has been shown to lower or cease intercourse, thus lowering self-esteem and resulting in negative effects on sexual functioning and interpersonal relationships.

A potential contributor to deep dyspareunia in women with endometriosis that is largely under-researched is the concept of central sensitization. Central sensitization is an amplification of nociceptive signaling that may result from prolonged pain causing sensitization of the dorsal horn neurons, which results in hyperalgesia (increased response to pain) and allodynia (response to pain when there normally

would not be). A recent study, comparing cross-sectional data from suspected or surgically diagnosed endometriosis patients, suggested that bladder and pelvic floor tenderness may be markers of central sensitization. However, the linkage between the indirect markers of central sensitization and the presence of central sensitization requires confirmation. This link can be assessed through validated quantitative sensory testing (QST). Likewise, the association between central sensitization and deep dyspareunia may also be confirmed through QST. QST is an objective measurement tool to determine the presence and/or degree of sensory disturbances, by detecting the alterations in nociceptive pathways. For example, a low pain-pressure threshold (i.e., increased pain sensation) at healthy unaffected areas, as measured by QST, indicates central sensitization.

---

## RESEARCH OBJECTIVES

---

**Purpose:** To determine if there is an association between bladder and pelvic floor tenderness, and measures of central sensitization, and if measures of central sensitization are associated with deep dyspareunia.

**Research Question:** Does an increased severity of deep dyspareunia result in a decreased pain-pressure threshold (measure of central sensitization)?

**Objectives:**

**Primary Objective:**

- 1) Examine the correlation between central sensitization and severity of deep dyspareunia.

**Secondary Objectives:**

- 1) Examine the correlation between central sensitization and severity of non-sexual pains and Endometriosis Health Profile (EHP-30) scores.
- 2) Examine the correlation between central sensitization and tenderness of the bladder and pelvic floor (determined by physician on physical exam).
- 3) Examine variations in severity of deep dyspareunia in women with the same disease state of endometriosis.

**Research Hypothesizes:**

**Primary Hypothesis:** Central sensitization (measured by pain-pressure threshold) is associated with an increased severity of deep dyspareunia, as well as a tenderness of the bladder and pelvic floor, in women with endometriosis.

**Secondary Hypothesis:** Women with endometriosis will have a great central sensitization (indicated by a lower pain-pressure threshold) than women without endometriosis.

**Outcome:** Central sensitization (lower pain-pressure threshold) will be strongly and positively correlated with the severity of deep dyspareunia, and will also be associated with bladder and pelvic floor tenderness.

---

## RESEARCH DESIGN/PROCEDURES

---

### Setting

The Pelvic Pain and Endometriosis program at the BC Women's Health Centre uses an interdisciplinary approach to managing pain, including: physiotherapy for bladder and pelvic floor, surgical intervention, pain education and medical management. This program addresses multiple factors influencing pain through multiple approaches, as opposed to the traditional approach of surgical removal of the endometriosis to resolve the pain alone.

### Design

This study is a longitudinal, prospective cohort study, involving cases and controls. The analyses will be carried out within cases, while the controls are primarily used for troubleshooting and optimization of the QST. We will collect data prior to the test date (QST appointment) and data on the test date (for cases and controls), as well as six weeks of daily survey completion after the test date, for cases only.

Primary Outcome: Severity of deep dyspareunia

Secondary Outcomes: Severity of superficial dyspareunia, severity of non-sexual pains, sexual quality of life (EHP-30)

Main Independent Variables: Central sensitization (measured by pain-pressure threshold (PPT) determined through QST)

Study Population: The case population includes women who have consented to the Data Registry (H16-00264) and who are new or re-referred to the BC Women's Health Centre for Pelvic Pain and Endometriosis, and who have, regardless of the severity of deep dyspareunia, either: 1) previous surgical diagnosis of endometriosis or 2) current ovarian endometrioma cyst or 3) current endometriosis nodule.

Sample Size: 126 cases and 50 controls. Due to the nature of the testing in this study and the fact that participants may not benefit directly from participating in this study, it is difficult to estimate the percentage of individuals who will take part in this study. However, we estimate that it will take approximately 6 months to recruit our desired sample size of 176 participants, and we will be assessing the recruitment rate throughout the study period. At the Centre, we see approximately 300 patients meeting the criteria for this study per year.

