#### Quantitative Sensory Testing (QST):

##### Case and Control:

- After the questionnaire has been completed, the participants will undergo QST to measure their pressure-pain threshold (PPT), the point where the sensation of pressure has changed to the sensation of pain (or first report of discomfort). This procedure will take approximately 30 minutes. Before testing begins, it will be made clear that the participants can withdraw from the study even during the procedure if they find it too uncomfortable.
- The PPT data will be written down on a paper copy with the unique study ID, and entered into an encrypted excel file.
- The testing room will be at a temperature between 20 and 25 degrees Celsius, with no fans or open windows, and no stressful stimuli (e.g., no loud noises or blinking lights). The participants will be sitting on a chair when QST occurs and before testing they will be asked if they are comfortable.
- QST, to measure PPT, will be done using an Electronic Thimble Algometer (purchased from the University of North Carolina). The Electronic Thimble Algometer consists of a calibration load cell and a force sensing resistor (FSR), as well as an amplifier which "reads" the force from the resistor and transfers the data to the connected computer (a laptop). The calibration load cell will be calibrated using 2 weights (0kg and 0.5kg) (Fisher Scientific, Cat #:S01369), as per the manufacturers recommendations. The FSR will then be calibrated on the load cell. The calibrations will ensure the accuracy and reliability of the measurements. Four test sites will be measured: left deltoid muscle, right deltoid muscle, and left first dorsal interosseous muscle and right first dorsal interosseous muscle. All test sites will be measured twice; therefore, the PPT will be measured eight times. The test sites will be measured bilaterally and duplicated to obtain an average value. The order of the test sites will be measured randomly (done automatically by

the Electronic Thimble Algometer). The investigator will describe the process of this test to the participant, following this script:

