#### DATA ANALYSIS

---

The data collected from the 30 case participants was used to execute a power analysis to determine the total sample size required for the study. With power=0.80 and  $\alpha=0.05$  two tailed, a sample size of 126 case participants was needed.

For the cases, statistical analysis following collection of the data will be done using a Spearman Correlation determine if there is significant association between PPT and the primary outcome (deep dyspareunia) and secondary outcomes (e.g. non-sexual pain). Mann-Whitney association may be done for the bladder and pelvic floor variables to determine if they are significantly associated with PPT. Multiple Variable Regression may be done using variables significantly associated to determine if they are independently associated, independent of possible confounders. Comparison of PPT between cases and controls will also be done, but the main reason for the controls is for troubleshooting of the QST.

---

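### The recruitment target equals the number the power analysis needs, so the stated power of 0.80 holds only if no recruited case is lost from the primary correlation

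*Combined protocol and SAP*

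**What the plan says.** The data analysis section reports a power analysis based on data already collected from 30 cases, at power 0.80 and two-sided alpha 0.05, and concludes that "a sample size of 126 case participants was needed". It does not give the correlation assumed. The primary analysis is a Spearman correlation, within cases, of PPT with deep dyspareunia.

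The Design section, under Sample Size, sets "126 cases and 50 controls". On timing it says "we estimate that it will take approximately 6 months to recruit our desired sample size of 176 participants", and on supply "At the Centre, we see approximately 300 patients meeting the criteria for this study per year". It also says that uptake is hard to predict, that participants may not benefit directly, and that the recruitment rate will be assessed during the study.

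The section on quantitative sensory testing (QST) says that "participants can withdraw from the study even during the procedure if they find it too uncomfortable", and the script read to participants repeats this. Cases then complete daily surveys for six weeks. In Appendix C, the survey item on pain at deep penetration has a response option for no intercourse. The plan gives no allowance for non-evaluable cases and no replacement rule in either direction.

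**The concern.** A power calculation gives the number of observations that must enter the analysis. Here that number is also the number to be recruited. A case contributes to the primary correlation only if she has both a usable PPT and a deep dyspareunia score, and the plan foresees ways in which one may be missing. A woman may stop during QST and leave no complete PPT. If the diary supplies the deep dyspareunia score, a woman who stops the diary, or who reports no intercourse throughout, has no value for the primary outcome. At stake is whether the study has the power it states. A null correlation from a study believed to have 80% power will be read with more confidence than the evaluable number justifies.

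**Working it through.** **Inputs from the documents.** Cases needed, 126; power, 0.80; alpha, 0.05 two-sided (data analysis section). Cases to recruit, 126; eligible women, about 300 a year; recruitment period, about 6 months (Design, Sample Size). Cases already collected, 30 (data analysis section).

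**Not in the documents.** The correlation assumed, the share of non-evaluable cases, and the uptake. The last two are treated below as assumptions over a range.

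**Step 1: the plan's own 126.** By Fisher's z, N = ((1.960 + 0.842)/atanh(r))² + 3. No r is stated, so the 126 cannot be checked forwards. Solved backwards, atanh(r) = 2.802/√123 = 0.2526, so |r| = 0.247. With the 1.06 variance factor often used for Spearman's coefficient, |r| = 0.254; with the Bonett-Wright factor, 0.251. The 126 is thus not reproducible from the text, which is different from being wrong.

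**Step 2: power if 126 are recruited and some are not evaluable.** Power = Φ(atanh(r)·√(n − 3) − 1.960). With r set so that n = 126 gives 80%, this becomes Φ(2.802·√((n − 3)/123) − 1.960). A constant variance factor cancels, so the choice among the three versions in Step 1 does not change the result.

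| Assumed loss | Evaluable n | Power | Recruit to keep 126 evaluable, 126/(1 − d) |
|---|---|---|---|
| 0% | 126 | 80.0% | 126 |
| 5% | 120 | 78.0% | 133 |
| 10% | 113 | 75.5% | 140 |
| 20% | 101 | 70.6% | 158 |

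**Step 3: the recruitment period (secondary).** Eligible women in 6 months: 300 × 6/12 = 150. Controls are left out because they are recruited from other sources.

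- If all 126 cases come from this window: 126/150 = 84% uptake.
- If the 30 cases count and predate the window: (126 − 30)/150 = 96/150 = 64% uptake.

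Months needed = cases/(300 × uptake) × 12. At an assumed 50% uptake this is 10.1 months for 126 cases and 7.7 for 96. At 40% it is 12.6 and 9.6.

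**The case against.** The strongest reply is that several stronger readings, which a reader might infer, are not in the text.

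- **Recruitment closes at 126 enrolled and no one is replaced.** The plan does not say this. It is silent, and continuing until 126 are evaluable is compatible with both sections. An agreement by telephone need not fill a place either, since written consent is signed at the test visit.
- **Every kind of loss lowers power.** Stopping the diary matters only if the diary supplies the primary score. Sexual pain is also scored on the test-day questionnaire, before QST, and the linked registry holds questionnaires completed before the physician appointment. The data analysis section does not say which source is used.
- **Withdrawal is provided for at every step.** The explicit text covers QST only.
- **The 6 months is a window that only 84% uptake could fill.** It is an approximate estimate, with the rate under review, and not a stopping rule. Slow uptake would first mean longer recruitment, with no loss of power. The 84% also falls to 64% if the 30 cases count, which the reference to a total sample size makes a natural reading. As 126 is below 150, there is no arithmetic contradiction.

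All of this stands, and it narrows the point. It does not remove it: nothing says whether the 126 are enrolled or evaluable, the number recruited equals the number needed, and at least one route of loss, withdrawal during QST, does not depend on the source of the pain score.

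**Conclusion.** The point holds in a limited form. The stated power of 0.80 is correct only if every recruited case yields both a usable PPT and a primary deep dyspareunia score. If recruitment were to close at 126 enrolled, power would be about 78%, 75% and 71% at 5%, 10% and 20% loss. The loss rates are assumptions, and the calculation takes it that 126 gives exactly 80% power for the correlation the investigators had in mind. At small losses the shortfall is modest. It grows if the diary is the source of the primary score, because a completed diary may still hold no value.

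The documents do not support saying that the study will be underpowered, or that the target cannot be reached in 6 months. The period is an optimistic forecast, implying 84% uptake (64% if the 30 cases count and predate the window) in a study whose own text calls uptake hard to estimate. That is a matter of feasibility and secondary to the power statement.

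**What to change.** - In Design (Sample Size) and the data analysis section, define the 126 as cases with both a usable PPT and a primary deep dyspareunia score, and close recruitment on that count. Name the source of that score, so that the count can be made.
- If recruitment must instead close at 126 enrolled, replace the stated power of 0.80 with the power at the expected evaluable number, and give the loss rate assumed.
- State the correlation used in the power analysis, and whether the 30 cases count toward the 126.
- Restate the recruitment period from 300 eligible women a year with an explicit assumed uptake, and say what follows if the monitored rate falls short.

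The cost is protocol wording and either a somewhat longer recruitment period or a slightly lower stated power. For example, at 10% loss about 140 cases would be recruited in place of 126. No procedure is added, and the evaluable target is unchanged.

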### **Inclusion Criteria:**

Case:

- Consented to participate in the Data Registry (H16-00264) prior to their physician appointment at the BC Women's Health Centre.
- New or re-referred to the BC Women's Health Centre for Pelvic Pain and Endometriosis.
- Endometriosis (previously surgically diagnosed, or current endometrioma, or current nodule)

- Willing and committed to indicating pain scores and menstrual data on a REDCap survey every day for 6 weeks after the test date.
- At least 18 years old

Control:

- Reproductive aged female with no suspected or diagnosed endometriosis.
- Have not experienced any sexual pain scores over 4/10 on a 11-point numeric rating scale, as determined on an online questionnaire prior to test day.
- At least 18 years old

### **Exclusion Criteria:**

Case and Control:

- Fibromyalgia.
- Severe and enduring psychological illness(es) affecting cognition (e.g., bipolar disorder, schizophrenia etc.).
- Currently pregnant or breastfeeding.
- Have a peripheral or central neurological disorder.
- Have diabetes mellitus or neuropathic pain.
- Do not speak English.\*
- Have had previous physical trauma (ex. Surgery) to the test site(s) (deltoid muscle in the shoulder, and first dorsal interosseous muscle).

\*Patients who do not speak English will be excluded to maintain the safety and wellbeing of the patient, as not understanding the test and process may put the patient in harm, as well as maintaining the validity of the results. We do not have research funding for a translator.

### **Recruitment and Data Collection prior to Test date:**

Case:

- At the end of their appointment with one of the endometriosis specialists at the BC Women's Health Centre for Pelvic Pain and Endometriosis, the physician will ask the patient if they are interested in learning more about this research study (if the physician deems them acceptable to be included based on screening of inclusion and exclusion criteria). The physician will provide the patient a copy of the consent form to read at home and will ask the patient if [name] or her delegate can call them in the next couple of days. Physicians will emphasize that participation is optional and does not influence their health care.

- A poster introducing the study will also be available in the clinic waiting rooms.
- Potential participants will be encouraged, if they feel comfortable doing so, to discuss the consent form with family, friends, and/or their physician. The potential case participants will be given a minimum of 24 hours to review the consent form before being contacted by [name] or her delegate.
- [name] will collect the physician forms and will confirm that the interested potential case participants consented to the data registry. [name] will only give [name] the contact information of the potential case participants that consented to the data registry. During the first phone call, [name] or her delegate will ask if the potential case participant is interested in participating in the study, and will explain the study and consent process, if they wish. During this phone conversation, [name] will remind the potential case participant that they have consented to the data registry, and consent to this study allows us access to analyze their data registry data. Verbal consent will be given if the potential case participant would like to participate, and a test appointment will be booked. [name] or her delegate will log the participant into the test computer during the test day so that they can complete the test day questionnaire online.
- Case participants will sign the consent form in-person at the beginning of the test day appointment.
- Note that the case participants do not need to complete the Data Registry questionnaire again, since we will be linking to their previously completed Data Registry questionnaires done before their physician appointment.
- Participants will be instructed not to take analgesics within 24 hours before the scheduled test, nor to take opioids within 2 weeks before the scheduled test, nor to consume alcohol within 24 hours prior to scheduled test time. The participants will also be told to wear comfortable clothing with easy access to their shoulder for the scheduled appointment.

Control:

- Recruitment of the control group will be done by poster advertisement at the BC Women's Hospital. If they are interested in the study, potential participants will be asked to contact [name] (contact information on poster) to learn more about the study.
- In addition to a poster advertisement, the research assistant will circulate an invitation (via. email/social media) to an in-person information session open to all potential control participants who may be interested in the study.
- In-person information sessions and poster advertisement may also be done at the BC Children's Hospital, the BC Children's Hospital Research Institute (BCCHRI), and the University of British Columbia.
- An in-person information session includes: a short presentation about the research study and what is required of the control participants, and contact information will be left for the potential control participants if they would like more information/if they would like to participate.
- Recruitment of control participants may also be done through institutional research newsletters.

- [name] or her delegate will mention to participants in the study that their friends and family are welcome to contact us if they would like to participate, and will provide the participant a copy of the poster. This will happen at the final interaction between the participant and the research so they do not feel pressure.
- In addition, we will recruit via electronic forms of communication (e.g. institutional listservs (CRC net for the BC Children's Hospital Research Institution) or research/student groups).
- [name] or her delegate will provide the potential control participant with a copy of the consent form (in person or by email). Each potential control participant will be advised to carefully read the consent form, and to contact [name] with any questions about the information contained in the consent form. Potential participants will be encouraged, if they feel comfortable doing so, to discuss the consent form with family, friends, and/or their physician. The interested control participants will give [name] or her delegate their contact information via in person or email. They will be given a minimum of 24 hours to review the consent form before being contacted by [name] or her delegate who will ask if they would like to take part in the study.
- If the control participant expresses interest in the study after reading the consent form, [name] or her delegate will send them a link to access the REDCap screening questions indicating sexual and non-sexual pains, age, and history of fibromyalgia (see attachment). Each control subject will be assigned a de-identified unique study ID.
- Criteria will be assessed by screening questions. If the participants are eligible based on the screening questions (18 years or older, pain scores less than 4/10, and no fibromyalgia) then they will be asked if they would like to consent to the study (online consent). This online consent allows access to the data from the screening questions. If they are not eligible, or do not consent to the study their screening questions will not be analyzed. If the control participant consents online they will be asked to complete additional questions on REDCap (height, weight, etc. See attached).
- [name] will receive an email from REDCap once the control participant has consented online, and will contact the participant to book a test day appointment.
- If the control participant had not completed the pre-test questionnaire after one week, they will be sent an email reminder.
- On the test day, the consent participants will sign the same consent form in-person to consent to the testing procedures.
- Participants will be instructed not to take analgesics within 24 hours before the scheduled test, nor to take opioids within 2 weeks before the scheduled test, nor to consume alcohol within 24 hours prior to scheduled test time. The participants will also be told to wear comfortable clothing with easy access to their shoulder for the scheduled appointment.

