#### Procedures for Data Collection (on Test day)

#### **Questionnaire:**

#### Case and Control:

- Data will be collected during a scheduled appointment with [name] or her delegate. The research visit will take approximately one hour of the participant's time (not including travel time to and from the site). The visit will take place in a BC Women's Health Centre private room (4th floor of the Shaughnessy building at the BC Women's Hospital). Data collected will include an online questionnaire containing: today's date, score of sexual and non-sexual pains, first day of last menstrual period, any changes in medication since their last visit to BC Women's Health Centre, current hormonal suppression, date of last physician appointment, menstrual cycle data, last time they have had sexual intercourse and how many times have they had sexual intercourse in the last one month. The pelvic pain questions asked on this online questionnaire are modified from the Brief Pain Inventory Short Form. This questionnaire will be filled out on REDCap online using a desktop computer in the room.
- The testing room will be maintained at a temperature between 20 and 25 degrees Celsius, with no fans or open windows (may use a white noise machine), and no stressful stimuli (e.g., no loud noises or blinking lights).
- As the participant completes the online questionnaire, [name] or her delegate will set up the Algometer and calibrate the force sensing resistor (FSR). [name] or her delegate will answer any questions.

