#### Data Linking:

The Data Registry for Chronic Pelvic Pain and Endometriosis (H16-00264) collects a wide range of data from all consenting patients of the BC Women's Centre for Pelvic Pain and Endometriosis including those who undergo surgery at the clinic. Case participants in this study (Endometriosis deep dyspareunia and central sensitization) are therefore also listed in the Data Registry (they consent to both). This will allow for direct matching. A data access request will be sent to the research coordinator ([name]) to collect the case participant data from the Data Registry. The information provided to the Data Registry research coordinator for data linking includes: unique study ID, MRN, PHN, first and last name, and date of initial visit to BC Women's Health Centre. All the data from the Data Registry is being linked. This data will be placed in an encrypted excel file on the O: drive. The research coordinator will pull the appropriate information and replace the participants Data Registry REDCap ID with the unique study ID for this study and place the file back on the O: drive, where [name] or her delegate will have access to it. Data for both studies are kept on the BC Women's secure O: drive in separate password protected folders with restricted access to study team members; therefore the data transfer can be undertaken within the PHSA secure network.

Once data linkage is complete the linking spreadsheet sent to the Data Registry research coordinator will be permanently deleted as per UBC policy 85.

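### EHP-30 and pelvic tenderness appear to be recorded at an uncapped interval before PPT, and the analysis uses neither that interval nor interim treatment

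*Combined protocol and SAP*

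**What the plan says.** Secondary objective 1 correlates central sensitization with non-sexual pains and with EHP-30 scores. Secondary objective 2 correlates it with "tenderness of the bladder and pelvic floor (determined by physician on physical exam". The Design section names the EHP-30 as the sexual quality-of-life outcome and PPT as the main independent variable.

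On timing, Recruitment and Data Collection prior to Test date (Case) says that cases need not fill in the registry questionnaire a second time, because "we will be linking to their previously completed Data Registry questionnaires done before their physician appointment". The woman is recruited at the end of that appointment. She has at least 24 hours with the consent form, is then telephoned, and a test visit is booked.

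The Setting section describes a programme that uses "physiotherapy for bladder and pelvic floor, surgical intervention, pain education and medical management".

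The test-day questionnaire covers sexual and non-sexual pain scores, current hormonal suppression, the date of the last physician appointment and "any changes in medication since their last visit", among other items. The Data Analysis section plans Spearman correlations, an optional Mann-Whitney test for the tenderness variables, and an optional regression on confounders that it does not name. For the sample size it says that "a sample size of 126 case participants was needed", at 80% power and two-sided 5% significance.

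**The concern.** Two of the variables to be related to PPT appear to describe the woman as she was at or before her clinic visit. PPT describes her on a later day. Between the two dates she has been seen by a programme whose treatments include physiotherapy aimed at the structures scored in objective 2. Nothing requires PPT to be measured before treatment begins.

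If tenderness or quality of life changes in the gap, the correlation with PPT is likely to be weakened. If more severely affected women are treated sooner, or wait a different time for the test, the distortion need not be the same for everyone. A null result for EHP-30 or tenderness could then not be separated from a timing effect. This matters most for tenderness, which also appears in the study's Purpose, its Primary Hypothesis and its expected Outcome.

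**Working it through.** **1. Where each variable is recorded for cases**

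| Variable | Registry or clinic visit | Test day | Daily survey (Appendix C) |
|---|---|---|---|
| EHP-30 | only apparent source | not listed | not listed |
| Bladder and pelvic-floor tenderness | physician's examination | no examination listed | not listed |
| Non-sexual pain | not needed | scored | average pelvic pain scored |
| Deep dyspareunia | not needed | sexual pain scored | scored |
| PPT | no | measured | no |

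The first two rows are reached by elimination; no sentence states the source of either variable in the dataset. The Data Linking section says that all registry data are linked, which fits.

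**2. The interval.** The lower bound is the 24-hour consent period plus booking. The only upper limit in the text is the physician's request to telephone within a couple of days, and that limits the call, not the test. The instruction to take no opioids for two weeks before testing may lengthen the gap for some women.

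**3. What the analysis could use.** The test-day form records the last appointment date, hormonal suppression and medication changes. It lists no item on physiotherapy or surgery since the examination. The Data Analysis section mentions none of these.

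**4. The plan's own figure.** Inputs from Data Analysis: n = 126, power 0.80, two-sided alpha 0.05. No effect size is given, so 126 cannot be reproduced, only back-solved. With the Fisher z formula n = ((1.960 + 0.842)/atanh(r))² + 3:

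- atanh(r) = 2.802/√123 = 2.802/11.09 = 0.2526, so r = 0.247.
- With a variance factor of 1.06 for Spearman, r = 0.254.
- As a cross-check, a round r = 0.25 gives n = 124 (factor 1) or 131 (factor 1.06). So 126 is consistent with an r near 0.25.

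**5. Illustration for EHP-30.** Assume a same-day correlation of 0.247. Let s be the correlation of the clinic-time score with its test-day value (an assumption; the documents give none). If the earlier score relates to PPT only through the test-day score, the expected correlation is s × 0.247, and power = Φ(atanh(s × 0.247) × 11.09 − 1.960).

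| s | expected r | z − 1.960 | power at n = 126 | n for 80% power |
|---|---|---|---|---|
| 1.0 | 0.247 | 0.842 | 80% | 126 |
| 0.9 | 0.223 | 0.551 | 71% | 157 |
| 0.8 | 0.198 | 0.264 | 60% | 199 |
| 0.7 | 0.173 | −0.020 | 49% | 260 |

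The Spearman factor leaves these power figures unchanged to the nearest percent.

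**6. Illustration for tenderness.** Assume 63 women per group and a PPT difference of 0.5 SD. Assume also that 20% of women tender at the visit are no longer tender at QST and then have the non-tender group's mean PPT. The difference becomes 0.8 × 0.5 = 0.4 SD. Mann-Whitney power (relative efficiency 0.955) is Φ(d × √(0.955 × 63/2) − 1.960) = Φ(5.485d − 1.960). That is 78% at d = 0.5 and 59% at d = 0.4. Every input here is assumed.

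**7. A limit on the remedy.** Data Analysis reports that 30 cases had already supplied data. If they count towards the 126, an analysis using only a new test-day EHP-30 would have 126 − 30 = 96 cases. Power at r = 0.247 is then Φ(0.2526 × √93 − 1.960) = Φ(0.476) = 68%, below the 71% in the s = 0.9 row. Cases already tested should therefore not be dropped.

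**The case against.** The strongest reply is that much of this is inference. The source of the EHP-30 follows by elimination from a prose list, and the case questionnaire itself is not among the documents. Appendix A, which is said to illustrate the case procedures, is not legible in the text reviewed, so a time limit shown there cannot be ruled out. No passage says that treatment starts before QST, and the prompt telephone call suggests that many gaps may be short. This stands, and it is why the size of the effect is left open.

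The direction is also not guaranteed. The Background describes sensitization as arising from prolonged pain. If PPT changes slowly, an earlier EHP-30 might track it as well as a later one. This stands too: attenuation is likely, not certain.

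Three stronger readings are tempting and not supported:

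- A reader might infer that the whole of secondary objective 1, or the primary analysis, is mistimed. Non-sexual and sexual pain are both scored on test day, alongside PPT.
- A reader might infer that the linkage file's "and date of initial visit to BC" Women's Health Centre pulls an earlier episode's record for re-referred women. That date is listed with the study ID, record numbers and name as a matching identifier, and all registry data are linked.
- A reader might take the power figures as this study's power for the secondary objectives. The documents do not say that 126 was chosen for them, and they give neither the stability of the scores nor the length of the gap.

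It can also be said that the optional regression could adjust for the interval. It could in part, but neither the interval nor interim treatment is named, and physiotherapy and surgery are not listed for collection.

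**Conclusion.** The point holds for two secondary analyses: PPT against EHP-30, and PPT against bladder and pelvic-floor tenderness. Both appear to pair a clinic-time measure with a PPT taken later, with no visible limit on the gap and no planned use of the interval or of interim treatment. The likely effect is a weakened association, with confounding possible. The real size cannot be derived from the documents. The 71%, 60% and 49% figures show only how sensitive the EHP-30 analysis would be under the back-solved r = 0.247 and the assumed stabilities. No figure in the plan is contradicted. This is an inexpensive improvement to make, not a fault that undermines the study.

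**What to change.** 1. Add the EHP-30 to the test-day questionnaire for cases still to be tested, and make it the main score for the EHP-30 correlation. Keep cases already tested by using their registry score. Report the correlation based on the registry score for all cases as a sensitivity analysis.
2. Add one test-day item asking whether physiotherapy, surgery or any other treatment has started since the clinic examination.
3. Compute the interval from the recruiting clinic examination to QST. Use that examination's date and not automatically the last appointment, which may be a later visit. Report the tenderness comparison overall, and add a prespecified sensitivity analysis that adjusts for, or restricts on, the interval and interim treatment change. Any cut-off for the interval should be fixed before the data are examined; the documents support no particular value.

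The cost is a few minutes of participant time on a computer already in use and a few added analyses, with no new visit or examination. The drawbacks are mixed EHP-30 timing for cases already tested and a smaller sample in any restricted analysis.
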